## 13 OTHER APPROVALS, PERMISSIONS, and REGULATORY ISSUES

**13.1 Other regulatory approvals.** Identify any other regulatory approvals that are required for this research, by checking applicable boxes

*Do not attach the approvals unless requested by the IRB.*

Approval	Research for which this is required
 Radiation Safety	Procedures involving the use of radioactive materials or an ionizing radiation producing machine radiation, if they are conducted for research rather than clinical purposes. Approvals need to be attached to the Supporting Documents page in Zipline .
 Institutional Biosafety	Procedures involving the transfer/administration of recombinant DNA, DNA/RNA derived from recombinant DNA, or synthetic DNA.
 RDRC	Procedures involving a radioactive drug or biological product that is not approved by the FDA for the research purpose and that is being used without an IND, for basic science research (not to determine safety and effectiveness, or for immediate therapeutic or diagnostic purposes).
 ESCRO	Procedures involving the use of some types of human embryonic stem cells.

**13.2 Approvals and permissions.** Identify any other approvals or permissions that will be obtained. For example: from a school, external site/organization, funding agency, employee union, UW Medicine clinical unit.

*Do not attach the approvals and permissions unless requested by the IRB.*

n/a

**13.3 Financial Conflict of Interest.** Does any member of the team have ownership or other Significant Financial Interest (SFI) with this research as defined by [UW policy GIM 10](#)?

 **No**

**Yes**

→ If yes, has the Office of Research made a determination regarding this SFI as it pertains to your proposed research?

 **No**

→ If no, contact the Office of Research [contact], [[contact]](mailto:[contact])) for guidance on how to obtain the determination

 **Yes**

→ If yes, upload the Conflict Management Plan for every team member who has a FCOI with respect to the research, to the **Supporting Documents** page of **Zipline**. If it is not yet available, use the text box to describe whether the Significant Financial Interest has been disclosed already to the UW Office of Research and include the FIDS Disclosure ID if available.

**E-TIPS Trial**

## Statistical Analysis

Out of 202 participants, 11 (5.4%) were missing their 12-week Pain Interference Score. Because our analysis plan stipulated that if greater than 5% of the primary outcome was missing, we would consider if there were significant predictors for missing the outcome, we conducted this analysis and found that having multiple diagnoses (chi-squared p-value = 0.038), having a higher baseline Average 7-day Pain Intensity Score (Wilcoxon rank sum p-value = 0.025), baseline Pain Catastrophizing Score (Wilcoxon rank sum p-value = 0.002), and baseline PROMIS Pain Interference Score (Wilcoxon rank sum p-value = 0.017) were all significant in predicting missing data at 12 weeks. We then used Heckman's selectivity models of pattern-mixture models with multiple imputation to account for our missing data. Given that our missingness percentage was on the boundary of our set plan, a standard multiple imputation analysis assuming missingness at random was also considered and was consistent with the Heckman's selectivity model approach. All models were multivariable linear models, adjusted for the randomization stratification characteristics of site (UW or AbilityLab), sex (Male or Female), and baseline severity (Average 7-day Pain Intensity Score < 7), and condition (MS, Spinal Injury, Traumatic Brain Injury, Amputation, or Multiple Diagnoses). To assess if there was a difference from baseline in the Pain Interference Score, the outcome was modeled as the 12-Week Pain Interference Score, controlling for baseline. The outcome of observed Pain Interference Score at week 12, the difference from week 12 to baseline, the percentage difference, and a whether a 10-point decrease was achieved were also analyzed, using two sample t-tests or the Chi-squared test, presented along with means, standard deviations, and standardized mean differences.

The continuous secondary outcomes at week 12 were analyzed similarly, with multiple imputation models to account for missing data, and adjusted for the same set of covariates. P-values were adjusted using a Bonferroni correction. Further follow-up outcomes at month 6

were analyzed using mixed effects models with repeated measures. The outcomes at baseline, week 6, week 12, and month 6 were included, with the same covariates as above included as fixed effects: treatment, time point, treatment by time point interaction, site, sex, baseline severity of pain, and condition. An exponential spatial correlation structure was used as the assessments were not equally timed. Contrasts across treatment and across time points were calculated.

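### The 10-point responder outcome has only an unadjusted chi-squared test, with no imputation mentioned; it should use the imputed data and covariates of the primary model

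*SAP*

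**What the plan says.** The SAP's Statistical Analysis section reports the amount of missing primary-outcome data: "Out of 202 participants, 11 (5.4%) were missing their 12-week Pain Interference Score". It recalls a trigger, "our analysis plan stipulated that if greater than 5% of the primary outcome was missing", beyond which predictors of missingness would be examined. Four were found: multiple diagnoses (p = 0.038), baseline pain intensity (p = 0.025), baseline catastrophizing (p = 0.002) and the baseline value of the primary measure itself: "baseline PROMIS Pain Interference Score (Wilcoxon rank sum p-value = 0.017) were all significant in predicting missing data at 12 weeks".

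The response was imputation: "We then used Heckman's selectivity models of pattern-mixture models with multiple imputation to account for our missing data", with a missing-at-random multiple imputation as a check. The models are linear and "adjusted for the randomization stratification characteristics of site", sex and baseline severity, and also for condition. The week-12 model controls for baseline pain interference as well.

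Four further versions of the outcome follow: the observed week-12 score, the change, the percentage difference and achievement of a 10-point decrease. These "were also analyzed, using two sample t-tests or the Chi-squared test", shown with means, SDs and standardised mean differences. No covariate, stratum or imputation is mentioned for them. The rest of the SAP covers continuous secondary outcomes and mixed models for follow-up; it contains no other responder analysis.

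**The concern.** The section sets its own standard for the primary outcome (baseline, stratification factors, imputation) because missingness was found to depend on baseline. The responder outcome is a dichotomy of the same score, yet the text does not bring it under that standard. People with high baseline scores are more often missing and also have the most room for a 10-point fall, so leaving them out lowers the responder rate in each arm.

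At stake is the clinical-relevance statement, not the efficacy test. The protocol (section 1.8b) supports the intervention partly with the share of earlier participants who had a clinically meaningful reduction: 33% to 47% across trials and 36% in the TIPS trial. Those figures concern pain intensity, but a 10-point responder rate in pain interference would probably be used in the same way.

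**Working it through.** **The SAP's own figure.** 11/202 = 5.4%, which reproduces. The 5% trigger is 0.05 × 202 = 10.1 participants, so 11 just exceeds it; 191 are observed. The documents give no SD, correlation, responder rate or effect size. Everything below that needs one rests on an assumption.

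**Week-12 score and change already have an adjusted result.** If Y − B = a + τT + βB + e, then Y = a + τT + (β + 1)B + e. The treatment coefficient τ is the same whether the outcome is the week-12 score Y or the change Y − B, given baseline B as a covariate. The primary model therefore supplies both.

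**Precision of the unadjusted versions.** With baseline correlation ρ:
- SE(raw)/SE(adjusted) = 1/√(1 − ρ²): 1.15 at ρ = 0.5 and 1.25 at ρ = 0.6.
- SE(change)/SE(adjusted) = √(2(1 − ρ))/√(1 − ρ²): 1.15 and 1.12.

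This loss falls on supplementary tests whose precise counterpart is already reported.

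**Direction of error from ignoring the strata.** If the strata explain R² of the outcome, the true size of a nominal 0.05 t-test is about 2(1 − Φ(1.96/√(1 − R²))). For R² = 0.05, 0.10, 0.20 and 0.30 this is 0.044, 0.039, 0.028 and 0.019. The tests are conservative.

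**Responder rates under baseline-dependent missingness.** Assume SD 6, ρ = 0.6 and mean falls of 4.5 and 2.0 points. The SD of change is 6 × √(2 × 0.4) = 5.37.
- Full data: 1 − Φ(5.5/5.37) ≈ 15% and 1 − Φ(8/5.37) ≈ 7%. The simulated values are 15.2% and 6.8%, a difference of 8.4 points.
- About 5.5% missing, strongly concentrated at high baseline: 14.1% and 6.1%, a difference of 8.0 points.
- Missingness as strong as the SAP's p-value suggests: p = 0.017 gives z = 2.39. SE(AUC) = √(203/(12 × 11 × 191)) = 0.090, so AUC = 0.5 + 2.39 × 0.090 = 0.71, or about √2 × Φ⁻¹(0.71) = 0.8 SD. The simulated rates are then about 14.6% and 6.5%, a difference of about 8.2 points before rounding.

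With 101 per arm, the SE of the full-data difference is √(0.152 × 0.848/101 + 0.068 × 0.932/101) = 4.4 points. A shift of 0.2 to 0.4 points is at most a tenth of that.

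**Gain from the adjusted, imputed responder model.** Simulation under the same SD and correlation, with about 5% missing at higher baseline, gives about 1 to 3 power points, with the SE of the risk difference essentially unchanged. The exact figure depends on the settings; read it as a small gain.

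**Sensitivity to the 11 missing values.** Assume 101 per arm, 5 and 6 missing, and 29/96 against 14/95 responders:
- complete cases: 15.5 points, p = 0.010
- missing counted as non-response: 29/101 − 14/101 = 14.9 points, p = 0.010
- worst case: 29/101 − 20/101 = 8.9 points, p = 0.14
- best case: 34/101 − 14/101 = 19.8 points, p = 0.001

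The extremes are bounds, not likely values, but they show why the handling should be stated.

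**Events per parameter in the proposed model.** Treatment, site, sex and severity take 1 each, condition (five categories) takes 4 and baseline takes 1, so 9 in all. At 15.2% and 6.8% there are about 101 × 0.152 + 101 × 0.068 = 22 events, or 2.5 per parameter. At 30% and 15% there are about 45, or 5 per parameter.

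**The case against.** The strongest reply is that nothing important rests on these tests. They follow an adjusted, imputed model with a missing-at-random check, and unadjusted comparisons beside an adjusted one are common and transparent. That stands, and it limits the point to one of presentation and consistency.

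Three stronger readings are tempting and are not supported:
- **That all four tests are complete-case.** The text says observed only for the week-12 score. For the other three, complete-case analysis is the natural reading because no imputation is mentioned, but it is not stated.
- **That the arm comparison is biased.** The predictors of missingness are reported for the pooled sample. With missingness that depends on baseline alike in both arms, simulated bias in the mean difference is about zero. Bias would need missingness that differs by arm or an effect that varies with baseline; the documents neither show nor exclude these.
- **That a fifth to a third of the sample is in effect thrown away.** The SE ratios correspond to 20% to 36%, but for continuous outcomes that already have an adjusted estimate, and with assumed correlations. They do not carry over to the responder outcome.

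The reply does not remove the gap for the responder outcome, which has no adjusted or imputed version to fall back on.

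**Conclusion.** The point holds in a narrow form and is minor. The 10-point decrease is tested only by an unadjusted chi-squared test, in a section that found baseline-dependent missingness and dealt with it by adjusted imputation for the continuous score. The primary conclusion is not affected and type I error is not inflated. A change would bring consistent missing-data handling, an explicit statement of how the 11 missing values enter the responder rate, and about 1 to 3 power points. The power figure and the shift of 0.2 to 0.4 points in the difference rest on assumed values (SD 6, correlation 0.6; for the shift, also mean falls of 4.5 and 2.0 points) that the documents do not give.

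**What to change.** 1. Derive responder status in each existing imputed dataset from the imputed week-12 score and the baseline score. Fit a logistic model with treatment, site, sex, baseline severity, condition and baseline pain interference. Pool the results and report a standardised risk difference with its confidence interval.
2. Label the unadjusted tests of week-12 score, change and percentage difference as descriptive, and refer to the baseline-adjusted model for the treatment effect on score and change.
3. State which participants enter the chi-squared test and how the missing values are counted.
4. Because the SAP already reports the missingness results, mark the logistic model as an added supplementary analysis and show it beside the chi-squared result.

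The cost is one model on data that already exist and a few sentences. The downside is the low number of events per parameter (about 2.5 to 5 under the rates assumed above). A fallback such as penalised likelihood should be named before the model is fitted.

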**Aim 1: Evaluate the efficacy of the telehealth pain self-management intervention, adapted for employees with physical disability, ("E-TIPS"), relative to a waitlist control in reducing pain interference (primary outcome) in adults with chronic pain and physical disability.**

Hypothesis 1.1. Participants randomized to E-TIPS will report greater improvements in pain interference (primary outcome, measured by PROMIS Pain Interference Scale) compared to participants assigned to control at post-treatment (12 weeks post-randomization, primary endpoint).

Hypothesis 1.2. Improvements in pain interference will be maintained at 6 mo. post randomization.

Although the long-term goal is to promote job retention and enhance employment in employees with chronic pain, we chose pain interference as the primary outcome due to its high association with disability and our ability to detect meaningful change within the study timeframe. We will conduct exploratory analyses to determine whether reductions in pain interference are associated with fewer missed days of work and other employment outcomes.

**Aim 2: Examine the effects of E-TIPS compared to control on secondary outcomes relevant to work, including self-efficacy for pain management, pain intensity, fatigue, mood, and days worked at 12 weeks post-treatment and maintenance of effects at 6-month follow up.**

Hypothesis 2.1. Participants randomized to E-TIPS will report greater short-term (post-treatment) improvements in secondary outcomes compared with control.

Hypothesis 2.2. Participants assigned to E-TIPS will retain treatment benefits at 6-months.

Hypothesis 2.3. Within-subject outcome changes during the 12-week intervention period will be greater than during the waitlist time period.

**Aim 3: Evaluate factors, including treatment adherence, treatment satisfaction, and barriers/facilitators of implementation relevant to future dissemination and large-scale**

**implementation of E-TIPS in employed individuals with physical disabilities and chronic pain.** We will collect measures of treatment adherence, satisfaction, and convenience from participants allocated to E-TIPS. We will assess barriers and facilitators to implementation from the participants' perspectives by collecting information about other factors that influence participation.

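### Week-12 secondary outcomes are adjusted by single-step Bonferroni; Holm on the same family keeps the same familywise control and can only add rejections

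*SAP*

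**What the plan says.** **Week 12.** After describing the primary model, the SAP (Statistical Analysis) states: "The continuous secondary outcomes at week 12 were analyzed similarly", with multiple imputation and the same covariates. The next sentence is "P-values were adjusted using a Bonferroni correction". No family size, alpha or adjusted threshold is given. Protocol section 1.5, Aim 2, gives as examples of secondary outcomes "self-efficacy for pain management, pain intensity, fatigue, mood, and days worked". Section 5.15 lists further measures, such as sleep disturbance and pain anxiety.

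**Month 6.** The SAP fits a mixed model with a treatment-by-time interaction: "The outcomes at baseline, week 6, week 12, and month 6 were included". It ends: "Contrasts across treatment and across time points were calculated". It does not link a contrast to a hypothesis. Protocol section 1.5 has Hypothesis 1.2, "Improvements in pain interference will be maintained at 6 mo. post randomization", and Hypothesis 2.2, that E-TIPS participants keep their gains at six months.

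**Limits of the text.** The SAP refers to an earlier plan ("Because our analysis plan stipulated that if greater than 5% of the primary outcome was missing"). That plan is not among the documents, and one part of the SAP was removed before review.

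**The concern.** Bonferroni holds every outcome to alpha/k whatever the other outcomes show. Hypothesis 2.1 expects E-TIPS to do better on several secondary outcomes, which is the setting where a single-step rule gives up most. Once one null hypothesis has been rejected, the remaining ones no longer need the full penalty, and Holm uses this.

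What is at stake is individual week-12 effects that are real but miss the Bonferroni threshold. The error rate is not at stake, because Bonferroni protects it.

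Month 6 is a smaller matter. A reader cannot tell from the SAP which of the calculated contrasts answers the two durability hypotheses.

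**Working it through.** **Inputs.** The plan has no figure of its own to reproduce on this point: no alpha, family size, threshold or power. The only related arithmetic is the missing-data count. 11/202 = 5.45%, printed as 5.4%, which leaves 202 − 11 = 191 observed.

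Assumed values:
- alpha = 0.05, two-sided
- k = 5, from the Aim 2 list, with a range of 4 to 10 (days worked may not count as continuous; section 5.15 names further measures)
- correlation 0.5 between test statistics
- 80% unadjusted power per real effect, so noncentrality 1.96 + 0.84 = 2.80

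**Thresholds at k = 5.** Bonferroni compares every p-value with 0.05/5 = 0.0100. Holm sorts the p-values, compares the i-th smallest with 0.05/(5 − i + 1), and stops at the first failure. Its thresholds are 0.0100, 0.0125, 0.0167, 0.0250 and 0.0500.

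**Why Holm never loses a rejection.** If the i-th smallest p-value is at most alpha/k, all smaller ones are too. Each Holm threshold is at least alpha/k, so Holm reaches and rejects it.

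**Why familywise error is held.** With m0 true nulls, the first true null that Holm could reject comes at step k − m0 + 1 or earlier, where the threshold is at most alpha/m0. The union bound gives m0 × alpha/m0 = alpha under any dependence.

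**Illustration (invented p-values).** For 0.004, 0.012, 0.016, 0.024 and 0.045, Bonferroni rejects one and Holm rejects five.

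**Bonferroni power by hand.** At k = 5 the critical value is 2.576. Power is about Φ(2.80 − 2.576) = 0.59, which agrees with the simulation below.

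**Simulation.** 400,000 trials per setting, equicorrelated normal statistics, average power per real effect:

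| k | Real effects | Bonferroni | Holm |
|---|---|---|---|
| 5 | 5 | 0.590 | 0.688 |
| 5 | 4 | 0.589 | 0.652 |
| 5 | 3 | 0.588 | 0.625 |
| 5 | 2 | 0.589 | 0.606 |
| 5 | 1 | 0.589 | 0.589 |
| 4 | 4 | 0.619 | 0.709 |
| 10 | 10 | 0.499 | 0.608 |
| 10 | 5 | 0.498 | 0.529 |

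For a smaller effect, take a standardized difference of 0.3 with 191 participants in equal arms. Noncentrality is 0.3 × √(191/4) = 2.07 and unadjusted power is 0.545. With k = 5 and all effects real, power is 0.308 (Bonferroni) against 0.373 (Holm).

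**What does not change.** Holm's first step is the Bonferroni threshold, so the chance of at least one rejection is the same. With k = 5 and all effects real it is 0.892 for both. Holm lost no Bonferroni rejection in any setting, and its familywise error with some effects real was 0.025 to 0.040.

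**Month 6, by reading.** The SAP model has baseline among its outcomes and a treatment-by-time interaction. The between-arm difference in change from baseline to month 6 is therefore a linear combination of terms already fitted. It refers the result to baseline, as the week-12 primary model does by another route: "the outcome was modeled as the 12-Week Pain Interference Score, controlling for baseline".

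**The case against.** The strongest reply is that nothing here is wrong. Bonferroni is valid, and the SAP, written in the past tense, reports it as already applied. Holm would be chosen with results in hand, leaving readers two sets of adjusted p-values. The gain of about ten points needs every effect to be real, and alpha, k, correlation and power are all assumed. Holm also has no equally simple simultaneous intervals.

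Much of this stands. It is an efficiency point, the ten points are the best case, and the interval drawback is real. The late timing does less harm than usual: on a fixed family, whichever of the two methods is reported, the rejections are among Holm's, so familywise error stays at or below alpha. Confusion is avoided if Bonferroni remains the stated adjustment and Holm is labelled as an addition.

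On month 6, a reader might infer that the durability hypotheses were tested with many contrasts at an unadjusted 0.05, inflating the error several-fold. The documents do not support that. No sentence says month-6 contrasts were read as confirmatory tests at that level. The Bonferroni sentence most naturally refers to week 12, but does not delimit its family. Protocol section 1.5 already puts the week-12 endpoint first and treats month 6 as maintenance. The earlier plan may set the rule. Nor can one say month 6 lacks an analysis, since the fitted model supplies the needed contrast.

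**Conclusion.** The point holds as an improvement worth making, not as an error in the analysis. A reader might take the heading to mean that the Bonferroni results are unsound; they are not, and every Bonferroni rejection stands.

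That Holm dominates Bonferroni needs no assumption. The size does. Under the stated assumptions with k = 5, the gain in average power is about 10 percentage points if all effects are real (0.688 − 0.590), about 4 if three are (0.625 − 0.588), about 2 if two are (0.606 − 0.589) and none if one is. With all effects real it is about 9 points at k = 4 and 11 at k = 10. At a standardized difference of 0.3 and k = 5 it is about 6 to 7 points. The unstated k and alpha also prevent a reader from checking the adjustment.

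Month 6 is a minor clarification. What is missing is missing only from the text available.

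**What to change.** **Week 12.** Keep the Bonferroni-adjusted p-values as the stated adjustment. Beside them:
- print Holm-adjusted p-values for exactly the family already used, neither enlarged nor reduced
- state that family's members, k and alpha
- label Holm as added after results were known, and mark any claim that rests on Holm alone
- report confidence intervals unadjusted and say so

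**Month 6.** State that Hypotheses 1.2 and 2.2 are read from the between-arm difference in change from baseline to month 6, and label the secondary-outcome contrasts exploratory. If the earlier analysis plan already fixes these points, cite it instead.

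**Cost.** A few SAP sentences. Holm values come from the existing unadjusted p-values: multiply the i-th smallest by k − i + 1, carry the running maximum forward, and cap at 1. The month-6 contrast needs no refit. The lasting drawback is that the intervals will not match the adjusted p-values.

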**Hypothesis 3.1.** Participants allocated to E-TIPS will demonstrate high treatment adherence (defined as attending > 6/8 sessions) and report being highly satisfied with the treatment (> 8 on 0-10 numeric rating scale).

**1.6 Study design.** Provide a one-sentence description of the general study design and/or type of methodology.

*Your answer will help HSD in assigning applications to reviewers and in managing workload. Examples: a longitudinal observational study; a double-blind, placebo-controlled randomized study; ethnographic interviews; web scraping from a convenience sample of blogs; medical record review; coordinating center for a multi-site study.*

We propose a randomized (1:1), single blind parallel-group trial comparing the TIPS telehealth pain self-management intervention, adapted to address employment issues (E-TIPS), to a waitlist control in adults with physical disabilities and chronic pain who are employed.

**1.7 Intent.** Check all the descriptors that apply to your activity. You must place an "X" in at least one box.

*This question is essential for ensuring that your application is correctly reviewed. Please read each option carefully.*

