After the 6-month assessment, the usual care group will be offered treatment. While in usual care, participants are free to continue or start any treatment they decide. It is not necessary that they refrain from seeking out mental health or other services.

We will randomly select up to 20 participants proportionally to the diagnostic group domain included in the broader sample and interview them about their experience with E-TIPS treatment. As this is qualitative research, the final sample size will be determined by the point we reach thematic saturation, meaning the point when we are no longer learning new information about the topic/question at hand. We will interview participants by audio-only Zoom using an interview guide. Audio-only Zoom has been selected for ease of recording and

obtaining transcripts for analyses. We will ask participants what they found helpful and not helpful about their treatment and about the barriers and facilitators to the treatment. We will then perform a content analysis.

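### The month-6 mixed model does not adjust the between-arm effect for the outcome's own baseline score, so its interval is wider than the data allow, by an amount that depends on an unreported correlation

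*SAP*

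**What the plan says.** The SAP's Statistical Analysis section describes two models.

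- **Week 12 (primary).** A linear model in which "the outcome was modeled as the 12-Week Pain Interference Score, controlling for baseline". The outcome's own baseline score is a covariate.
- **Month 6.** A mixed model with four response times: "The outcomes at baseline, week 6, week 12, and month 6 were included, with the same covariates as above included as fixed effects". The listed fixed effects are "treatment, time point, treatment by time point interaction, site, sex, baseline severity of pain, and condition". The own-baseline score is not among them, and nothing states that the arms share a baseline mean. The correlation structure is exponential in time.

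The only baseline pain term in the month-6 model is the stratification factor, "baseline severity (Average 7-day Pain Intensity Score < 7", a two-level cut of pain intensity. On the month-6 treatment effect the published text says only: "Contrasts across treatment and across time points were calculated".

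The month-6 comparison is still a randomized one. Protocol section 5.1 states: "After the 6-month assessment, the usual care group will be offered treatment".

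**The concern.** With treatment, time and their interaction all free, the model fits a separate mean for each arm at each visit. With complete data, the month-6 arm difference is then close to an unadjusted difference in means. The arm difference in change from baseline is a change-score analysis. Neither uses the baseline score with its optimal weight, as the week-12 model does.

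Aim 2 in Protocol section 1.5 asks about effects relative to control and whether they last to 6 months, and month 6 is the last visit at which the arms can be compared as randomized. A wider interval there makes a lasting effect harder to show or to rule out, although the baseline score needed to narrow it has been collected. The SAP gives no reason for treating the two time points differently.

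**Working it through.** **Inputs.** From the documents: 202 participants ("Out of 202 participants, 11 (5.4%) were missing their 12-week Pain Interference Score"; 11/202 = 5.4%, which agrees) and 1:1 allocation ("We propose a randomized (1:1), single blind parallel-group trial"). The documents give no month-6 SD, correlation, missingness or power figure, so there is no stated figure to reproduce. Assumed: baseline-to-month-6 correlation r = 0.3 to 0.7, equal variances, complete data.

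**Step 1: direction.** In common units, the variance of the between-arm month-6 effect is:

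- month-6 difference: 1
- difference in change: 2(1 − r)
- baseline-adjusted: 1 − r²

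The excess over the adjusted analysis is 1 − (1 − r²) = r² for the month-6 difference, and 2(1 − r) − (1 − r²) = (1 − r)² for the change. Both are positive for every r strictly between 0 and 1, so the direction does not depend on the contrast.

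**Step 2: size before allowing for severity.**

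| r | Month-6 difference, 1/(1 − r²) | Change, 2/(1 + r) |
|---|---|---|
| 0.3 | 1/0.91 = 1.10 | 2/1.3 = 1.54 |
| 0.5 | 1/0.75 = 1.33 | 2/1.5 = 1.33 |
| 0.7 | 1/0.51 = 1.96 | 2/1.7 = 1.18 |

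**Step 3: allow for the severity factor, which is in the model.** Let s be its correlation with the outcome's baseline score. Assume arms balanced on severity, and severity acting on month 6 only through baseline. The month-6 ratio becomes (1 − r²s²)/(1 − r²). Interval width is the square root of the ratio.

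| r | s = 0.3 | s = 0.5 | Extra width |
|---|---|---|---|
| 0.3 | 0.9919/0.91 = 1.09 | 0.9775/0.91 = 1.07 | about 4% |
| 0.5 | 0.9775/0.75 = 1.30 | 0.9375/0.75 = 1.25 | 12–14% |
| 0.7 | 0.9559/0.51 = 1.87 | 0.8775/0.51 = 1.72 | 31–37% |

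For pain intensity, severity is a cut of the same score. If 25% lie above the cut (assumed), s is about 0.73 and the ratios are 1.05, 1.16 and 1.45, or 2%, 8% and 20% extra width.

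In the difference in change, severity has one coefficient for all visits and cancels. The reported interval for the change therefore stays 24%, 15% and 8% wider (square roots of 1.54, 1.33 and 1.18).

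**Step 4: the better of the two contrasts.** At r = 0.3 and 0.5 it is the month-6 difference; at r = 0.7 it is the change. The extra width is about 4%, 12–14% and 8%, and for pain intensity about 2%, 8% and 8%. Dividing 202 by the variance ratio, the better contrast has the precision of a baseline-adjusted analysis of:

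- r = 0.3: 202/1.090 to 202/1.074, about 185–188 participants
- r = 0.5: 202/1.303 to 202/1.250, about 155–162
- r = 0.7: 202/1.176, about 172

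**Step 5: check under the SAP's correlation structure.** A simulation used exponential correlation at weeks 0, 6, 12 and 26, 202 participants, one severity slope for all visits, 30% in the high-severity level, unstratified allocation and 3000 runs per setting. When underlying pain intensity correlated 0.4 with the outcome's baseline, the variance ratios for the better contrast were 1.08, 1.26 and 1.17 (4%, 12% and 8% wider). When severity was a cut of the outcome itself they were 1.09, 1.18 and 1.19 (4%, 9% and 9%). The shared severity slope, which Step 3 ignores, can add up to 0.04 to the month-6 ratio.

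**Step 6: month 6 versus week 12.** Let z be the correlation between those visits and d the fall in baseline correlation from week 12 to month 6. Baseline adjustment removes a share d²/(2(1 − z)) of the variance of the between-arm contrast, and half of that within an arm. Under constant correlation d = 0, so nothing is lost. Under exponential decay with month 6 at week 26, the baseline correlations are z^(12/14) at week 12 and z^(26/14) at month 6:

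- z = 0.6: 0.645 − 0.387 = 0.258; 0.258²/0.8 = 8.3% between arms, 4.2% within
- z = 0.7: 0.737 − 0.516 = 0.221; 0.221²/0.6 = 8.1% between arms, 4.1% within

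**The case against.** The model is valid and unbiased, and baseline as a response has a use: one fit gives change from baseline at every visit, which suits contrasts across time points. That stands. The loss comes only from leaving the baseline arm means unconstrained, so a reader who inferred that the model is wrong because it includes baseline would be mistaken.

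Hypotheses 1.2 and 2.2 are worded as maintenance and can be read as month 6 against week 12, where the loss is small (Step 6). That also stands, though the 4–8% of variance under exponential decay is not nothing. The published text does not tie a contrast to either hypothesis; text that is not public may do so.

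The size rests on assumed correlations, and no month-6 precision target is shown to be missed. True. A reader might take the r = 0.7 entry in Step 2 (1.96) to mean intervals 40% wider and 202 participants reduced to the worth of 202/1.96, about 103. The documents do not support that. It ignores the severity factor that is in the model, and it presumes the month-6 difference was reported when the change contrast at the same r costs about 8%. Under pure exponential decay, r = 0.7 would also need a correlation of about 0.83 between week 12 and month 6.

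Finally, the analysis is already described in the past tense, and a re-analysis adds a second month-6 result for each outcome. This limits the remedy to a sensitivity analysis; it does not remove the loss.

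**Conclusion.** The point holds as one of precision. The between-arm month-6 effect is estimated less precisely than the collected data allow, and this is certain in direction for either contrast. The size is conditional on r, which is not reported. With r of 0.3 to 0.7 and severity correlated 0.3 to 0.5 with the baseline score, the better contrast has an interval about 4% to 14% wider (2% to 8% for pain intensity in the closed form). The less favourable contrast loses more: up to 31–37% for the month-6 difference at r = 0.7, and 24% for the change at r = 0.3. All figures assume equal variances and complete data.

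Three stronger inferences are not supported. The month-6 estimate is not biased, because the arms were randomized. The week-12 primary result is not affected, because that model controls for baseline. The month-6 comparison is not compromised by waitlist treatment, because usual care is offered it only after that assessment.

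**What to change.** For the between-arm month-6 effect, add a labelled post hoc sensitivity analysis beside the original result. Preferred form: model week 6, week 12 and month 6 as responses, with the outcome's own baseline score and baseline-by-time as covariates. Take baseline out of the responses in this version; the score should not be both response and covariate. Protocol section 5.1 places the baseline survey before randomization, so the covariate should be available for nearly everyone.

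Alternative: keep baseline as a response and constrain the arms to a common baseline mean. This keeps the change-from-baseline contrasts, but its adjustment depends on the fitted correlation structure, and it can lose part of the gain when severity is a cut of the same score. In the simulation at r = 0.5 its standard error was then 0.129 SD, against 0.123 with the covariate.

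Keep the original model for within-arm change from baseline. When reporting, say which contrast addresses Hypotheses 1.2 and 2.2. Present the added analysis as an estimate with its interval, not as a further confirmatory test.

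Cost: one re-analysis per outcome on data already collected. It is post hoc, so the original result must stay visible.
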